### ***5.2 Intention to Treat***

From the moment of randomization, the patient will be included in the trial irrespective of whether they receive the assigned treatment regimen. Similarly, all enrolled patients will receive clinical follow-up and will be included in the final analysis.

### ***5.3 Patient Numbering***

Upon randomization, each patient will be uniquely identified in the study by a five-digit identification number consisting of two parts, the two-digit center number (to be assigned by Vanderbilt University Medical Center) and the three-digit subject number. The investigator will assign patient numbers sequentially within each center (001, 002, 003...). Once assigned to a patient, a subject number will not be re-used and will remain with the patient throughout the study. Subjects meeting all inclusion/exclusion criteria will be randomized to one of the two treatment groups. If the patient has signed the informed consent form and then fails to be randomized for any reason, the reason for not being randomized will be entered on the Screening and Enrollment Log.

If subjects have more than one aneurysm that qualifies for the trial, each aneurysm will be assigned a subject number since each aneurysm will be randomized separately.

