## **4.2 Exclusion Criteria**

1. Patient has more than one aneurysm requiring treatment in the current treatment session, and only one of those to-be treated aneurysms fits the FEAT inclusion criteria (i.e., - if either (1) a patient has multiple aneurysms, but only one will be treated at enrollment; or (2) if two or more aneurysms are treated during the current treatment session and BOTH are able to be enrolled, then they remain eligible for the trial. Non-treated additional aneurysms may be treated at a later date with any coil type that the operator chooses).
2. Target aneurysm has had previous coil treatment or has been surgically clipped.
3. Hunt and Hess score is 4 or 5 after subarachnoid hemorrhage.
4. Inability to obtain informed consent.
5. Medical or surgical co-morbidity such that the patient's life expectancy is less than 2 years.

Death or procedural/disease-related morbidity may result in some subjects not having follow-up angiography. For the primary outcome of angiographic recurrence, the analysis will be conducted 2 ways: (1) among only those patients with angiographic assessment at 12-18 months, and (2) among patients with angiographic assessment, plus those with death or procedural/disease-related morbidity that precluded angiography, with such patients counted as incident events. Similarly, for the secondary outcome of treatment-related morbidity and mortality, patients without angiographic evaluation due to death or procedural/disease-related morbidity will be counted as incident events in the analysis.

Use of coil-assist devices (stent, balloon, etc.) will be allowed. Intention to use such a device will be recorded pre-procedure, along with dome to neck ratio and rupture status.

Additional critical components of the study design include the large number of patients required to demonstrate a statistically significant difference, and the subsequent significant length of time required to allow enrollment. Therefore, we propose a three phase study design to address the following concerns:

- 1) A 6-year time window renders any conclusions irrelevant due to progress in technology. Typically the conclusions of long-term studies in the endovascular space are called into question because they do not include technology that is considered modern by the time the study is completed. Stryker has multiple coil iterations planned over the next 5 years. To not involve these new technologies would make the study non-viable to

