##### **Intent-to-Treat (ITT) Population**

The ITT population will consist of all randomized subjects grouped by their assignment at randomization regardless of whether or not they actually received the treatment to which they were assigned. This sample will be used for summaries and analyses of the primary endpoint and the secondary clinical endpoints. The ITT population will be used for all effectiveness analyses and descriptions of patient and baseline characteristics.

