##### **Safety Population**

The safety population will consist of all randomized subjects who initiate endovascular coiling, grouped by their assignment at randomization regardless of whether or not they actually received the coil size to which they were assigned. The safety population will therefore be identical to the ITT population if all randomized patients receive attempted vascular coiling. The safety population will be used to present safety summaries and for the analysis of safety data.

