## 6.4 Patient Characteristics

### 6.4.1 Patient Disposition

Disposition will be summarized in the screened and ITT populations.

Disposition summaries of the screened population will include:

- The number of patients screened
- The number and percentage of eligible patients randomized

Disposition in the ITT population will be summarized by randomization group and will include:

- The number of patients randomized
- The number and percentage of patients who received their assigned treatment
- The number and percentage of patients withdrawn or lost to follow-up by the 3 to 6 month visit and the primary reason for withdrawals
- The number and percentage of patients withdrawn or lost to follow-up by the final study visit at 12 to 18 months and the primary reason for withdrawals

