### 6.5.3 *Missing Primary Endpoint Data*

Patients without previous evidence of inadequate angiographic occlusion, either on the 3 to 6 month visit angiogram or on a clinically driven angiogram taken prior to study exit, that miss the 12 to 18 month angiogram, or whose 12 to 18 month angiogram is not readable by the core lab, will be missing the primary endpoint. Patients missing the primary endpoint who die prior to or during the 12 to 18 month visit window (up to 18 months post-randomization) and die with known cause of death related to their aneurysm or unknown cause of death will be considered treatment failures with inadequate occlusion. Patients missing the primary endpoint with a known cause of death unrelated to their aneurysm will be considered missing.

Patients with missing primary endpoint data will have their 12 to 18 month angiographic

occlusion status imputed via multiple imputation assuming that the data are missing at random. The imputation model will be stratified by randomization assignment and include age, sex, randomization strata for aneurysm status, randomization strata for wide neck status, aneurysm size, and angiographic occlusion status at the 3 to 6 month visit. Since this model includes a mixture of variables types (i.e. continuous and binary), a fully conditional specification method will be used (Berglund 2014).

The main feature of the imputation approach is the creation of a set of clinically reasonable imputations for angiographic occlusion for each patient with missing data. This will be accomplished using a set of repeated imputations created by predictive models based on the majority of participants with complete data. The imputation models will reflect uncertainty in the modeling process and inherent variability in patient outcomes, as reflected in the complete data. Thirty datasets will be imputed.

After the imputations are completed, all of the data (complete and imputed) will be combined and the analysis performed for each imputed-and-completed dataset. Rubin's method of multiple (i.e., repeated) imputation will be used to estimate treatment effect (Rubin 1986).

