### **6.6.1 *Neurologic Morbidity***

The number and percentage of patients who experience neurologic morbidity at 24-hours post-operation will be reported by randomization group. The proportion of patients with neurologic morbidity will be compared between groups using a log binomial model and differences between the groups will be summarized using relative risk and the corresponding 95% confidence interval.

Patients that die within 24-hours will be counted as having neurologic morbidity. Survivors missing the 24-hour NIHSS assessment will have their neurologic morbidity outcome imputed via multiple imputation assuming that the data are missing at random. The imputation model will be stratified by randomization assignment and include age, sex, randomization strata for wide neck status, randomization strata for aneurysm status, aneurysm size, and baseline NIHSS. Since this model includes a mixture of variables types (i.e. continuous and binary), a fully conditional specification method will be used (Berglund 2014). Thirty datasets will be imputed and Rubin's methods will be used to combine them and estimate treatment effect (Rubin 1986).

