### **6.6.2 *Survival***

Survival over the full duration of follow-up will be described using Kaplan-Meier curves and compared between the randomization groups using a log-rank test. The hazard ratio and corresponding 95% confidence interval for death in the larger coil group compared to the smaller coil group will be estimated using a Cox proportional hazards model. Patients who withdraw consent or are lost-to-follow up will be censored at the time of study exit. Time to event will be computed as the date of death (or the date of censoring) – randomization date. In cases where the patient dies or is censored the day they are randomized, the time will be coded as 0.5 days.

Causes of death and relatedness to the procedure will also be described by randomization group. The number and proportion of patients that have a procedure related mortality within 30 days post-procedure will be presented by group and group differences will be summarized as a relative risk with the corresponding 95% confidence interval.

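### One person with two enrolled aneurysms becomes two subjects, but the SAP has no person-level link, so death, mRS and 24-hour morbidity are entered twice (effect probably small, size unknown)

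*Combined protocol and SAP*

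**What the plan says.** Protocol 4.2 keeps a patient eligible "if two or more aneurysms are treated during the current treatment session and BOTH are able to be enrolled". Protocol 5.3 first describes the subject number as what identifies a patient, then says that for a person with several qualifying aneurysms "each aneurysm will be assigned a subject number since each aneurysm will be randomized separately". Such a person therefore holds two numbers and two independent-looking records.

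The SAP builds its populations on those numbers. For efficacy, "The ITT population will consist of all randomized subjects grouped by their assignment at randomization". For safety, "The safety population will consist of all randomized subjects who initiate endovascular coiling". The disposition table in SAP 6.4.1 lists "The number of patients randomized" and has no line for persons holding two numbers.

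The analyses are written per patient:
- **24-hour morbidity (6.6.1):** "The proportion of patients with neurologic morbidity will be compared between groups using a log binomial model".
- **Survival (6.6.2):** "compared between the randomization groups using a log-rank test", with a Cox model.
- **mRS (6.6.3):** a van Elteren test by arm, repeated by rupture status.
- **SAEs (6.7.2):** Poisson models with robust variance, no cluster named.
- **Primary endpoint (6.5.1):** a log-binomial model with no within-person term. Where the endpoint is missing, 6.5.3 counts deaths that are aneurysm-related or of "unknown cause of death will be considered treatment failures with inadequate occlusion".

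The only clustering term in the SAP is center, in one sensitivity analysis of the primary endpoint (6.5.4).

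**The concern.** Occlusion, re-treatment and packing density belong to an aneurysm. Death, mRS and a 24-hour NIHSS change belong to a person. When one person carries two subject numbers, a person-level outcome appears on both records. If the aneurysms were assigned to different arms, the same outcome is counted in each. If they were assigned to the same arm, that person counts as two.

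These are not peripheral endpoints. 24-hour morbidity and the 3–6 month mRS are the secondary hypotheses in the gatekeeping sequence (SAP 6.8). If rupture status is recorded per aneurysm, a person with one recently ruptured and one unruptured aneurysm supplies one mRS score to both stratum-specific tests in the last family.

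The primary endpoint is touched at one point: an unknown-cause death with a missing endpoint becomes a failure on both records. For an aneurysm-related death this depends on whether relatedness is judged per aneurysm, which the SAP does not say. Nor does it say under which number an SAE attributable to neither aneurysm is counted, although Protocol 7.2.2 requires reporting regardless of causality.

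At stake are correct counts and correct standard errors for the clinical and safety comparisons.

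**Working it through.** **The plan's own figure.** With 325 per arm, 73% v 82% and two-sided alpha 0.05 (SAP 6.5.2), power is 78.6%, in line with the stated approximate 80%. That figure is not in dispute here.

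**Inputs.** From the documents: 650 records and 1:1 allocation. Assumed, because the documents give no value: the share f of persons with two enrolled aneurysms, taken as 2%, 5% and 10%; the chance that a pair is split across arms; and a 10% person-level event rate in the simulations.

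**Counts.** Persons = 650/(1+f). Pairs = f × persons. Share of records that come from pairs: s = 2f/(1+f). With independent 1:1 assignment, half of the pairs are split.

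| f | Persons | Pairs | Split pairs | s |
|---|---|---|---|---|
| 2% | 637 | 12.7 | 6.4 | 0.039 |
| 5% | 619 | 31.0 | 15.5 | 0.095 |
| 10% | 591 | 59.1 | 29.5 | 0.182 |

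At an assumed 5% death risk, the deaths expected to appear in both arms number 6.4 × 0.05 = 0.3, 15.5 × 0.05 = 0.8 and 29.5 × 0.05 = 1.5.

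**Type I error, person-level endpoint.** True variance relative to the variance the SAP would use is 1 + ρs[P(same arm) − P(split)], with ρ = 1 because both records carry the same outcome.
- Independent assignment: 1 + s × (0.5 − 0.5) = 1.00, so about 5%.
- All pairs split, f = 10%: 1 − 0.182 = 0.818. Type I error = 2Φ(−1.96/√0.818) = 3.0%.
- All pairs in the same arm, f = 10%: 1 + 0.182 = 1.182. Type I error = 2Φ(−1.96/√1.182) = 7.1%.

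Simulations at the 10% share agree: 2.9–3.5% when all pairs are split and 6.9–7.5% when all share an arm. At a 5% share the simulated extremes are 3.9% and 5.7%. With variance clustered on person, simulated type I error returns to about 4.7–5.6% in every allocation scenario.

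**Size of the estimate, independent assignment.** This depends on how the effects of two treated aneurysms combine in one person.
- *They average* (a split person gets half the effect). Split records are s/2 = f/(1+f) of all records and contribute no difference. The effect shrinks by 2.0%, 4.8% or 9.1%; at a 10% share, an assumed 6.0 points becomes 6.0 × (1 − 0.091) = 5.5.
- *They add* (a same-arm pair carries twice the effect). The estimate is (1 − s) × Δ + (s/2) × 2Δ + (s/2) × 0 = Δ, so 6.0 points stays 6.0.

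Dilution at a 10% share is therefore anywhere from 0 to 9%.

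**Primary power.** The same variance formula applies to occlusion, with ρ below 1. Under independent assignment the factor is 1.00 and power stays at 78.6%. At a 10% share with ρ = 0.5, power would be 82.3% if all pairs were split and 75.0% if all shared an arm.

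**The case against.** **Criterion 8 bars it.** Inclusion criterion 8 requires that the patient has not already been randomized into this trial. Read literally, it rules out a second number. But Protocol 4.2 and 5.3 provide for the case expressly, so the texts conflict and double enrolment cannot be assumed away.

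**It is too small to matter.** Much of this stands. The share is unknown, the expected number of duplicated deaths is about one at most in the middle scenarios, and primary power hardly moves. The SAP may be revised before data lock, and identifiable source documents are already uploaded, so linkage is feasible. That supports a modest rating and a cheap fix. It does not support leaving the rule unwritten, since a rule chosen after the arm of a duplicated death is known would be post hoc.

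**Readings that go too far.** A reader might infer any of the following:
- *The plan biases clinical effects toward zero.* That needs the two aneurysms' effects to average. The documents do not say so, and if effects add there is no dilution.
- *Dropping only the split persons restores the true effect.* If effects add, it overstates it. With same-arm pairs counted once, at a 10% share: 6.0 × (1 − s/2)/(1 − 0.75s) = 6.0 × 0.909/0.864 = 6.3 points.
- *False positives are inflated, or are certainly at 5%.* Either depends on the allocation algorithm. Protocol 5.5 says only that it stratifies, and SAP 3.1.2 adds site. Restricted allocation could split pairs more than half the time.
- *The SAP prescribes double counting.* It is silent; the double entry follows from populations defined by subject number.

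**Conclusion.** The point holds. Under the rules as written, one person can hold two separately randomized numbers, and the SAP's populations and models then count that person's death, mRS and 24-hour morbidity twice, with variances that assume independent records. An unknown-cause death with a missing primary endpoint is a failure on both records.

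The effect is probably small. Its size cannot be fixed from the documents, because neither the share of two-aneurysm persons nor the allocation algorithm is given. At an assumed 10% share and 10% event rate, type I error for a person-level endpoint lies between about 3% and 7.5% across the allocation extremes, and near 5% under independent assignment. Dilution under independent assignment is 0–9% at that share. Nothing here shows that the primary comparison is compromised. This should be corrected, but it is not a threat to the trial's main conclusion.

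**What to change.** In the SAP, before data lock:

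1. **Link and count.** Add a person identifier across subject numbers. In 6.4.1, report by number how many persons hold two numbers and how many are split across arms. If there are few, this alone largely settles the matter.
2. **Cluster on person.** Keep every record in ITT. Use person-clustered variance in the log-binomial, Cox and Poisson models and a person-clustered version of the mRS comparison. In tables of deaths, mRS and SAEs, state persons and aneurysms separately.
3. **One sensitivity analysis.** Repeat the person-level endpoints, and the primary analysis as regards failures assigned because of death, in persons with a single enrolled aneurysm. This does not depend on how two aneurysms' effects combine.
4. **Reconcile the texts.** State whether 650 counts persons or aneurysms, and reconcile inclusion criterion 8 with Protocol 4.2 and 5.3.

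**Cost.** Modest extra programming, no new data and no one removed from ITT. Clustering corrects the standard error, not any dilution in the estimate; item 3 addresses that. Precision is lower in the sensitivity analysis only: records fall to 650(1 − s) = 625, 588 or 532 at shares of 2%, 5% or 10%, so standard errors rise by a factor of 1/√(1 − s), or about 2%, 5% or 11%.

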### ***5.4 Patient Recruitment***

Eligibility will be assessed once the neurovascular team makes a decision on endovascular treatment of an aneurysm. A Screening and Enrollment Log of all screened patients, consented patients, randomized patients, and completed patients will be kept and maintained in the study's electronic data capture system. If a patient meets inclusion and exclusion criteria, a suitable member of the research team will discuss the trial and provide the patient or their acceptable surrogate with written information. This person will allow the patient or acceptable surrogate adequate time to consider inclusion in the trial, and will answer all questions regarding the trial. If a patient/acceptable surrogate agrees to participate in the trial and signs the informed consent document, the patient will be randomized. One copy of the signed informed consent document will be given to the patient, one retained by the local investigators and a copy uploaded into the secure web-based database maintained by the coordinating center.

## **5.5 Randomization**

1. A research team member authorized to randomize will then perform randomization via a web-based randomization process. The randomizer will communicate the result of the randomization to the neurointerventionalist who will coil the aneurysm. Alternatively, the neurointerventionalist can perform the randomization prior to performing the procedure.

2. An algorithm that stratifies the randomization will be used to ensure balance between the two treatment groups on those parameters known to significantly affect the ability to coil and pack densely. The stratification of these variables is as follows:

- Aneurysm status of recently ruptured (within 15 days) versus not recently ruptured;
- Current trial phase
- Dome to neck ratio:
  - Not wide neck – dome to neck ratio  $\geq 2$ , or neck width  $< 4\text{mm}$
  - Wide neck – dome to neck ratio  $< 2$ , or neck width  $\geq 4\text{mm}$

3. Both treatment arms are anticipated to have approximately equal proportions of acutely ruptured aneurysms. Aneurysm location will be recorded but will not be a basis of stratification due to lack of location as contributing to the recurrence or packing density achieved.

## 6. Visit schedule and Assessments

### 6.1 Visit Schedule

	Screening and Enrollment	Embolization Procedure	Discharge	3-6 Month Follow-Up	12-18 Month Follow-Up	Unscheduled Visit(s)
Informed Consent	X					
Inclusion/Exclusion	X					
Randomization	X					
Chart Review	X					
Hunt Hess	X					
Fisher (if applicable)	X					
WFNS (if applicable)	X					
Modified Rankin	X		X	X	X	X
NIHSS			X	X	X	X
Research Data Collection	X	X	X	X	X	X
Clinical Evaluation	X		X	X	X	X
Imaging		X		X	X	X (if indicated)
Embolization		X				
Re-Treat (if applicable)				X	X	X
Evaluate for AEs/SAEs	X	X	X	X	X	X

### 6.2 Assessments

#### 6.2.1 Angiographic assessment

1. Procedural angiograms (as part of standard of care) will be collected at enrollment and follow-up. Follow-up angiograms should be performed at 3-6 months and again at 12-18 months post-coiling. De-identified JPEG files of the imaging will then be uploaded into the electronic data-capture system and sent to the core lab for evaluation and subsequent analysis. Images should show measurements or a dime should be placed for scale.

2. An independent core lab, not affiliated with Vanderbilt University Medical Center, will review and analyze all uploaded images. The core lab, using standard criteria and being blinded to treatment arm will confirm (1) aneurysm size/volume and dome to neck ratio, and (2) degree of occlusion at the end of treatment and on follow-up imaging. Digital subtraction angiography (DSA) or MRA are required for the 3-6 month and 12-18 months follow-up angiogram.

3. Volumetric filling will be determined by the core lab based on measurements of the aneurysms relative to dimes, and of the coils used provided by participating centers on the procedure case report form.

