## **5. Treatment Protocol**

### **5.1 Methods**

#### 5.1.1 Clinical methods

1. Patients randomized to the framing treatment arm will have an initial 0.014-0.0155” framing coil placed. Following this coil, additional 0.014-0.0155” framing coils may be placed, in a “Russian doll technique”, and as recommended, until the treating physicians deem, in their best clinical judgment, that a transition to smaller, 0.010” or 0.012” bare platinum coils, is appropriate. Following placement of the primary framing coil (per the randomization assignment), further coil placement is at the treating physician’s clinical discretion, until satisfactory aneurysm occlusion is obtained. However, treating physicians are encouraged to use as many 0.014-0.0155” framing coils as they determine are safe and clinically appropriate. Patients randomized to the control arm will have bare platinum coils less than 0.014” placed into the aneurysm only, under the operator’s discretion, until satisfactory aneurysm occlusion is obtained.

2. Coiling of aneurysms will be performed according to the standard of care at each institution. Choice of catheters, guide wires and other devices will not be dictated. However, non-bare-platinum coils, such as bioactive or hydrogel coils, may NOT be used in this protocol.

3. For ruptured aneurysms, the use of heparin and anti-platelet agents and the timing of their use will be according to treating physician preference.

4. For unruptured aneurysms, use of and choice of anti-platelet agents will be according to treating physician preference and local standard of care.

5. If, during the course of the procedure, the operator determines that it would be safer to use other coils or devices, such as bioactive or hydrogel coils, patient safety should take precedence over the randomly assigned treatment protocol. Reasons for protocol deviations, which are anticipated to be infrequent, will be recorded in the eCRF.

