#### 5.1.2 Research methods

1. Investigators should only randomize patients if they believe they can actually treat the patient equally safely and effectively regardless of the presence or absence of a 0.014-0.0155” platinum coil(s).

2. As far as possible, the intention is to exclusively use 0.014-0.0155” bare platinum coils for the initial coil in the Eighteen coil treatment arm and for as many subsequent coils as safe and appropriate, as determined by the treating physician. However, if for any reason a treating physician needs to forego placement of a 0.014-0.0155” coil or use a different coil for this purpose, the patient will remain in the study according to the intention to treat principle. Conversely, in patients assigned to the non-Eighteen coil treatment arm, no 0.014-0.0155” platinum coil is to be placed. However, if for any reason the treating physician determines he/she needs to place a 0.014-0.0155” bare platinum coil, the patient will remain in the study according to the intention to treat principle.

3. JPG’s of de-identified images will be uploaded for independent evaluation and stored in the study’s electronic database. These images will be reviewed by an independent, blinded core lab.

4. An electronic case report form (eCRF) will be completed at the end of the procedure. The procedural details collected for the eCRF will include findings of angiographic anatomy, size, location, neck size and dome-to-neck ratio .

5. At time of discharge, any adverse events will be recorded on the eCRF.

6. Data on any further aneurysm treatment or re-treatment of the study treated aneurysm will be collected during the study period.

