#### 3.1.2 Randomization and Masking

Patients will be randomly assigned in a 1:1 allocation to receive either larger or smaller coils. Patient randomization will be stratified by clinical site, aneurysm status (recently ruptured versus not), and dome to neck ratio (wide neck versus not). Randomization will be performed centrally through a web-based data collection system that automates the delivery of the randomization assignments.

Investigators will not be blinded to treatment assignment due to the nature of the treatment intervention. Investigators will, however, be blinded to all data from other clinical sites. Clinical outcome assessments will be completed by certified research staff that are not part of the treatment team. All angiograms will be analyzed by a blinded angiogram core laboratory personnel who will be blinded to clinical outcomes. Trial oversight will be provided by an independent Data and Safety Monitoring Board (DSMB).

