### 5.2.4 Packing Density

- Volumetric filling of the aneurysm, reported as a percentage and calculated using AngioCalc ([www.angiocalc.com](http://www.angiocalc.com)).

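### Protocol 6.2.1 gives the core lab that must grade occlusion blind to arm the coil measurements that reveal the arm, and neither document separates or sequences the two tasks

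*Combined protocol and SAP*

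**What the plan says.** **Blinding.** Under protocol 6.2.1 item 2 the core lab, "being blinded to treatment arm will confirm (1) aneurysm size/volume and dome to neck ratio, and (2) degree of occlusion", does so for the end of treatment and for follow-up imaging. Protocol 5.1.2 item 3 says of the uploaded images: "These images will be reviewed by an independent, blinded core lab". SAP 3.1.2 says: "All angiograms will be analyzed by a blinded angiogram core laboratory personnel who will be blinded to clinical outcomes". The only item that the SAP sentence names as masked is clinical outcome.

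**Packing density.** Protocol 6.2.1 item 3 reads "Volumetric filling will be determined by the core lab based on measurements of the aneurysms relative to dimes", and continues "and of the coils used provided by participating centers on the procedure case report form". SAP 5.2.4 defines the endpoint as "Volumetric filling of the aneurysm, reported as a percentage and calculated using AngioCalc" and does not say who does the calculation.

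**What separates the arms.** Under protocol 5.1.1 item 1, the framing arm starts with a 0.014-0.0155 inch coil. For the other arm the text is "Patients randomized to the control arm will have bare platinum coils less than" 0.014 inch, and no others. Item 5 of that section expects deviations to be infrequent.

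**Role of the reading.** Protocol 3.1 has the core lab determine the primary outcome. SAP 5.1 counts Raymond 1 or 2 as success. One inadequate reading at 3-6 months, at 12-18 months or on a clinically driven angiogram makes the patient a failure.

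**The concern.** Items 2 and 3 of protocol 6.2.1 conflict at the level of the core lab. One requires the lab not to know the arm, and the other supplies it with data from which the arm can be read. The Raymond grade is a visual judgement and the operators are not blinded (SAP 3.1.2), so the masked reading is the main protection of the primary endpoint against reader bias. Several readings per patient can decide the endpoint, and knowledge of the arm could act at each of them.

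The timing does not help. Procedural data are due within 72 hours of discharge (protocol 8.2), while the final imaging falls 10-20 months after coiling (protocol 5.1.3). The coil data therefore exist long before the decisive reading, and no rule holds them back from the lab.

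**Working it through.** **1. Do the coil measurements reveal the arm?** A coil treated as a cylinder of diameter d inches has volume per cm of length = (π/4) × (25.4·d)² × 10 mm³.

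- 0.010 inch: (π/4) × 0.254² × 10 = 0.51 mm³
- 0.012 inch: (π/4) × 0.3048² × 10 = 0.73 mm³
- 0.014 inch: (π/4) × 0.3556² × 10 = 0.99 mm³
- 0.0155 inch: (π/4) × 0.3937² × 10 = 1.22 mm³

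The same length of 0.014 inch coil has 1.96 times the volume of 0.010 inch coil. Filling cannot be computed without the diameter, so coil data adequate for item 3 show whether any 0.014-0.0155 inch coil was placed. Under protocol 5.1.1 that is the allocation, apart from deviations.

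**2. Is there a safeguard elsewhere?** Protocol 5.1.2, 5.1.3, 6.2.1 and 8.2 and SAP 3.1.2 and 5.2.4 were set side by side. None of them assigns the two tasks to different people, fixes their order, locks the Raymond readings or masks coil identity. By contrast, protocol 6.2.2 expressly bars the treatment team from administering the clinical scales. The protocol does write down a separation in that case.

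**3. The plan's own figure (background only).** SAP 6.5.2 gives 73% versus 82%, 325 per arm, two-sided 0.05 and approximately 80% power.

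- Pooled SE = √(2 × 0.775 × 0.225 / 325) = 0.03276
- Unpooled SE = √((0.73 × 0.27 + 0.82 × 0.18) / 325) = 0.03257
- Power = Φ((0.09 − 1.96 × 0.03276) / 0.03257) = Φ(0.792) = 78.6%

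This agrees with approximately 80%, so the same normal approximation is used below.

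**4. What a reading shift could do (illustration).** Take a true rate of 73% in both arms, 325 per arm, and an assumed net shift b in the readings of one arm, so that p1 = 0.73 and p2 = 0.73 + b. The two-sided rejection rate is

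Φ((b − 1.96·SE0)/SE1) + Φ((−b − 1.96·SE0)/SE1),

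with SE0 pooled and SE1 unpooled. For b = 0.03:

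- SE0 = √(2 × 0.745 × 0.255 / 325) = 0.03419
- SE1 = √((0.73 × 0.27 + 0.76 × 0.24) / 325) = 0.03417
- Rate = Φ(−1.083) + Φ(−2.839) = 13.9% + 0.2% = 14.2% (before rounding, 0.1416)

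| Assumed net shift | Patients affected (of 325) | Two-sided rejection rate (nominal 5%) |
|---|---|---|
| 1 point | 3.2 | 6.0% |
| 2 points | 6.5 | 8.9% |
| 3 points | 9.8 | 14.2% |
| 5 points | 16.2 | 31.6% |

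A 3-point shift is one third of the 9-point effect that the trial is designed to detect.

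**The case against.** A reader might infer that the primary endpoint reading is unblinded as the plan is written. The documents do not support that. They state in three places (protocol 5.1.2 and 6.2.1, SAP 3.1.2) that the reading is blinded. Item 3 names the core lab as an organisation. Nothing says that one person does both tasks, that the occlusion readers see the coil data, or that packing density is computed before follow-up images are graded. The lab's own procedures, which are not in these documents, may already keep the tasks apart. This objection stands, and it limits the point to a missing safeguard.

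Three further objections carry less weight.

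- **Received versus assigned.** Coil data show the treatment received, and protocol 5.1.2 item 2 keeps crossovers in their assigned arm. This is true, but with infrequent deviations the coils received still identify the arm for most patients.
- **Measurements, not a coil list.** The protocol speaks of coil measurements. The distinction makes no difference, because diameter is needed either way.
- **The SAP does not repeat the conflict.** SAP 5.2.4 does not assign the calculation to the core lab. Nor does it withdraw protocol 6.2.1 item 3.

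On size, the shift is assumed, and it presupposes that coil data reach the readers. Counting only results that favour larger coils would make a 1-point shift look like a near doubling, from 2.5% to 4.7%. The planned test is two-sided at 0.05 (SAP 6.1 and 6.5.1), and on that test the same shift adds about 1 percentage point.

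**Conclusion.** The concern holds as a gap in protection. A stated rule sends arm-revealing data to the lab whose reading decides the primary endpoint, and neither document sets a separation, an order or a lock. This goes beyond missing detail, because items 2 and 3 of protocol 6.2.1 cannot both be followed by the same reader without a safeguard that is not written down. The documents do not show that blinding has been lost.

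The size of any bias cannot be derived from the plan. The range of 6.0% to 31.6% against a nominal 5% rests on four assumptions: no true effect, 73% in both arms, 325 analysed per arm, and a net shift of 1 to 5 points in one arm only. It shows what a shift of that size could do and does not predict one. If the readers never see coil data, this route to a shift is closed.

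**What to change.** Amend protocol 6.2.1 item 3 and SAP 3.1.2 and 5.2.4 to say that:

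1. the core lab reports only aneurysm dimensions or volume and Raymond grades, and receives no coil data;
2. the coordinating center computes packing density from the core-lab volume and the eCRF coil log;
3. core-lab readers are blinded to treatment arm and coil data as well as to clinical outcomes.

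If the calculation has to stay with the core lab, the minimum is to lock all Raymond readings for a patient before that patient's coil data are released to the lab.

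The cost is wording plus moving one arithmetic step to a center that already manages the data (protocol 10.2). No extra reader, visit or procedure is needed, and the SAP allows revision before data lock. If the lab already separates the tasks, recording that takes a sentence.

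The SAP is dated 3/27/2024, and the documents do not say how many readings were complete by then. Wording cannot lock past readings. If coil data have already reached the occlusion readers, establish when, and report which readings were made after that point.
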